### PFIZER CONFIDENTIAL

CT24-WI-GL02-RF02 5.0 Non-Interventional Study Protocol Template For Secondary Data Collection Study 01-Aug-2023

- Hypertension
- Hyperlipidaemia
- Coronary artery disease/ischemic heart disease
- Chronic kidney disease
- Major surgery within 90 days before the index date
- Any malignancy
- NMSC
- HZ
- Human immunodeficiency virus (HIV)
- Serious infection
- Opportunistic infection
- Inflammatory/autoimmune diseases including other indications for the study drugs
  - Asthma
  - Allergic rhinitis
  - Systemic lupus erythematosus
  - Autoimmune thyroiditis
  - Psoriasis
  - Psoriatic arthritis
  - Celiac disease
  - Inflammatory bowel disease (IBD)
  - Vitiligo
  - Multiple sclerosis
  - Sjögren's syndrome
  - Sarcoidosis
  - Other indications for the study drugs
    - Rheumatoid arthritis
    - Atopic dermatitis
    - Juvenile idiopathic arthritis
- Ritlecitinib contraindications (to the extent measured in the databases)
  - Active serious infections including tuberculosis
  - Liver failure
- Pregnancy
- Bone fractures
- Osteoporosis
- Neurological events
  - Peripheral neuropathy
  - Sensorineural hearing loss
  - Migraine
  - Seizures and seizure disorders
  - Demyelinating disorders including multiple sclerosis
  - Neurodegenerative disorders

### PFIZER CONFIDENTIAL

CT24-WI-GL02-RF02 5.0 Non-Interventional Study Protocol Template For Secondary Data Collection Study 01-Aug-2023 Page 20 of 47 • Comorbidity as measured by a population-appropriate comorbidity index, such as Charlson Comorbidity Index (CCI). Use of disease risk scores may be considered for the exploratory objective.

Lifestyle factors, identified during the 12 months prior to and including index date

- Conditions related to alcohol misuse as a proxy for alcohol consumption, which is not recorded in the participating data sources
- Tobacco-related conditions as a proxy for smoking, which is not recorded in the participating data sources

### 9.3.4. Preliminary Operational Definitions of the Main Study Variables

Generally, in the participating data sources, disease is identified by diagnoses recorded at hospitalizations (all three countries) or at hospital-based specialist outpatient clinics (Denmark and Sweden). Diagnoses are currently coded using the World Health Organization (WHO) International Classification of Diseases, Tenth Revision (ICD-10). The Danish version of the ICD-10 may have more detailed codes compared with the WHO ICD-10. ICD-11 will be used if introduced during the study period. Treatment records originate, depending on the database, from outpatient dispensings, from hospital administrations, and are coded using the Anatomical Therapeutic Chemical (ATC) classification or local structured vocabularies (e.g., local treatment codes in Denmark).

Table 1 summarizes the initial operational definitions of the eligibility criteria, the exposure and the endpoints. The refined, country-specific definitions of all study variables as well as the final list of other variables with their operational definitions will be provided in the SAP.

Variable	Definition for all countries unless otherwise	Role in the analysis
	specified	
Age	In years	Eligibility criterion,
		demographic characteristic
Sex	Male, female, other	Demographic
		characteristic
Ritlecitinib	ATC code L04AF08	Exposure
Baricitinib*	ATC code L04AA37 (through 2023) L04AF02 (2024	Exposure
	onwards)	
	Treatment code BWHP106 (Denmark only)	
AA	ICD-10 code † L63	Eligibility criterion
Thromboembolic events	ICD-10 codes † I26, I260A I269A, I67.6, I74, I80.1,	Safety event of
(including DVT, PE,	180.2, 181, 182.0, 182.2; 182.3, 182.8, 182.9 022.3,	interest/endpoint
and arterial thrombosis)	087.0, 087.1, 0882D, 0882E, T817D	
HZ	ICD-10 codes † B01, B02, H031F, H131M, G051M,	Safety event of
	H190D, H192D, H190J, H220C, B027, B028, B029,	interest/endpoint
	G0511, H621B	
	ATC codes J05AB01 (HZ-specific tablet dose 800 mg	
	in package of 35 tablets based on product code)	
	J05AB11 (HZ-specific tablet dose: 500 mg based on	
	product code)	
	J05AB09 (HZ-specific tablet dose: 500 mg based on	
	product code) (23)	
Serious infection	ICD-10 codes† as the primary diagnosis at a hospital	Safety event of
	contact with a minimum of 1 overnight stay (24) A00-	interest/endpoint
	B99, D/3.3, E06.0, E32.1, G00-G02, G04.2, G05-G07,	
	H00.0, H44.0, H60.0-H60.3, H66-H67, H70, I30.1,	

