# 8.2. Primary Objective

The primary objective is to estimate the IRs of safety events of interest among patients with AA initiating ritlecitinib and patients with AA initiating baricitinib or other approved systemic treatments for AA in a real-world setting. The following are the primary safety events of interest:

- Thromboembolic events (including VTE and arterial thrombosis)
- Herpes zoster (HZ)
- Serious infections
- Opportunistic infections
- Malignancy
  - Malignancy excluding nonmelanoma skin cancer (NMSC)
  - o NMSC
- Major cardiovascular event (MACE)
- Neurological events of interest
  - Peripheral neuropathy
  - Sensorineural hearing loss
  - o Migraine
  - o Seizures and seizure disorders
  - o Demyelinating disorders including multiple sclerosis
  - o Neurodegenerative disorders
- Bone fractures
- Growth metrics in adolescents (height and weight, conditional on sufficient data available beyond age 12 years; Denmark only)

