### 9.3.2. Endpoints

The following endpoints (safety events of interest) will be assessed.

- Thromboembolic events, including:
  - VTE (including deep vein thrombosis [DVT] and pulmonary embolism [PE])
  - Arterial thrombosis (includes myocardial infarction [MI] and stroke)
- HZ
- Serious infections
- Opportunistic infections
- Incident primary malignancy, including:
  - Incident primary malignancy excluding nonmelanoma skin cancer (NMSC), overall and by major organ
  - Incident NMSC
- MACE\*, including (22):
  - o Nonfatal MI
  - Nonfatal stroke
  - Unstable angina
  - Hospitalization due to heart failure
  - Coronary revascularization by percutaneous intervention or coronary artery bypass graft
  - Cardiovascular death
  - \*Other MACE definitions (eg, excluding unstable angina, hospitalized heart failure, revascularization procedure) may be considered.
- Neurological events of interest (including the following events that are captured in at least one of the databases):
  - Peripheral neuropathy
  - Sensorineural hearing loss
  - o Migraine
  - Seizures and seizure disorders
  - Demyelinating disorders including multiple sclerosis
  - Neurodegenerative disorders
- Bone fractures

PFIZER CONFIDENTIAL

CT24-WI-GL02-RF02 5.0 Non-Interventional Study Protocol Template For Secondary Data Collection Study 01-Aug-2023 Page 18 of 47

- Growth metrics in adolescents
  - height and weight, conditional on sufficient data available beyond age 12 years (Denmark only)

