# Table 1. Preliminary Operational Definitions of the Main Study Variables

Variable	Definition for all countries unless otherwise	Role in the analysis
	specified	
MACE (22)	Definition for all countries unless otherwisespecifiedICD-10 codes† I20, I21, I60, I50, I11.0, I13.0, I13.2,I61, I62, I63, I64, H34Denmark and Sweden: Nordic Medico-StatisticalCommittee (NOMESCO) codes for coronary arterybypass graft (CABG) or percutaneous intervention(PCI):FNF, FNG, FNA, FNB, FNC, FND, FNEICD-10 codes I00-I99 as the underlying cause of deathin death certificates (cause of death registries)Due to longer lags for death certificate data, CV deathmay be defined based on death within 30 days of agiven diagnosis.France: CCAM procedure codes:For CABG: DDMA030, DDMA031, DDMA032,DDMA033, DDMA034, DDMA035, DDMA036,DDMA037, DDMA038, EPFA006, ENFA003For PCI: DDAF001, DDAF002, DDAF003,DDAF004, DDAF005, DDAF006, DDAF007,	Safety event of interest/endpoint
	DDAF008, DDAF009, DDAF010, DDAA002, DDFF001, DDFF002, DDLF001, DDPF002, DDSF001, YYYY082	
Bone fractures	ICD-10 codes M48.4, M48.5, M80, M84.3, M84.4, S02, S12, S22, S32, S42, S52, S62, S72, S82, S92, T02, T08, T10, T12, T14.2 (26). Additionally, surgery codes may be considered	Safety event of interest/endpoint
Neurological events of in	terest	
Peripheral neuropathy	ICD-10 codes: G60-G64, M54.1, G90.0	Safety event of interest/endpoint
Sensorineural hearing	ICD-10 codes: H90.3-H90.8, associated health services	Safety event of
loss	and devises may be considered	interest/endpoint
Migraine	ICD-10 codes: G43	Safety event of interest/endpoint
Seizures and seizure disorders	ICD-10 codes: G40, G41, P90, R56	Safety event of interest/endpoint
Demyelinating disorders including multiple sclerosis	ICD-10 codes: G35-G37	Safety event of interest/endpoint
Neurodegenerative disorders: Alzheimer, Parkinson, amyotrophic lateral sclerosis (ALS), spinal muscular atrophy (SMA), multiple system atrophy	ICD-10 codes: G12, G20, G23, G30	Safety event of interest/endpoint
Growth metrics conditional on sufficient data available beyond age 12 years	Denmark only: height and weight as recorded in the Danish Children's Database. Height and weight measures in adolescents will be benchmarked to geographically appropriate age and sex strata as percentiles in growth curves.	Safety event of interest/endpoint

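### Table 1 codes the primary thromboembolic endpoint without MI or stroke, although Section 9.3.2 counts both as part of it

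*Protocol*

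**What the plan says.** Section 8.2 lists "Thromboembolic events (including VTE and arterial thrombosis") among the primary safety events. Section 9.3.2 spells out the arterial part: "Arterial thrombosis (includes myocardial infarction [MI] and stroke").

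Table 1 in Section 9.3.4 then gives the codes. The label of the thromboembolic row names DVT, PE "and arterial thrombosis", so the row claims to cover the arterial part. Its three lines of codes read, in the text at hand, "I26, I260A I269A, I67.6, I74, I80.1", then "180.2, 181, 182.0, 182.2; 182.3, 182.8, 182.9 022.3", then "087.0, 087.1, 0882D, 0882E, T817D". In the last two lines the letters I and O have mostly been misread as 1 and 0, which is no fault of the plan.

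The MACE row of Table 1 opens with "I20, I21, I60, I50, I11.0, I13.0" and goes on to I61 to I64, among others.

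On the status of the table, Section 9.3.4 says: "Table 1 summarizes the initial operational definitions of the eligibility criteria, the exposure and the endpoints". Refined country-specific definitions are left to the SAP.

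**The concern.** One primary endpoint has two definitions in the same protocol. Under Section 9.3.2 a patient whose first event is an MI or a stroke has had a thromboembolic event. Under Table 1 the same patient has not, and stays at risk for that endpoint. The incidence rate of each safety event is the primary result of this study, so the choice of definition changes a primary result directly.

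The set-up of the study makes this harder to repair later. Under Section 9.6 the investigators in each country build their own analytic dataset and send only aggregate output, and individual data are not pooled. If one team works from Section 9.3.2 and another from Table 1, the country rates for this endpoint would not be comparable, and the coordinating centre could not recode them. Rates for the primary objectives also appear in all four interim reports (Section 6), so a mismatch would run through every report.

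**Working it through.** **1. Restore the code list.** Reading 1 as I and 0 as O, the thromboembolic row holds 19 codes: I26, I260A, I269A; I67.6; I74; I80.1, I80.2; I81; I82.0, I82.2, I82.3, I82.8, I82.9; O22.3; O87.0, O87.1; O882D, O882E; T817D. No reading of the damaged characters produces I21 or any of I60 to I64.

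**2. Compare it with the MACE row.** That row holds 12 diagnosis codes: I20, I21, I50, I60, I61, I62, I63, I64, I11.0, I13.0, I13.2 and H34. The two rows have no three-character category in common. The protocol's own MI and stroke codes are therefore all in the MACE row and none is in the thromboembolic row, where I74 is the only arterial category.

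**3. Look for a sentence that reconciles them.** Table 1 has no note that MI and stroke will be added to the thromboembolic row, and none that they count only under MACE. The row-specific promises to refine codes sit under serious infection and opportunistic infection, not here.

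**4. Reproduce the planning figures for this endpoint (Section 9.5).**
- Person-years: 74×8 + 96×7 + 110×6 + 127×5 + 144×4 + 161×3 + 123×2 = 3,864 per cohort; 2 × 3,864 = 7,728 at 1:1.
- Events: 7,728 × 1.17 / 1,000 = 9.04, stated as 10 (rounded up).
- Minimum HR = exp[2 × (1.96 + 0.84) / √events] = exp[5.60 / √9.04] = 6.45, stated as 6.4. Two-sided 5% and 80% power are my assumption, since the protocol gives neither. They also reproduce the other two stated values (6.66 and 4.33, against 6.7 and 4.3).

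The 10 events and the HR of 6.4 thus rest wholly on the Table 3 rate of 1.17.

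**5. Ask whether Table 3 can size the gap.** Per 1,000 person-years it gives thromboembolic events 1.17, ATE 2.50 and MACE 1.41.
- A composite that contained ATE as counted in Table 3 could not, on a common basis, have a rate below 2.50. So 1.17 does not contain it.
- Footnote b puts MI and both kinds of stroke inside MACE. On a common basis the rate of MI or stroke could then not exceed 1.41. So 2.50 is not the rate of MI and stroke.
- Table 3 has no definition of ATE, no separate rate for MI or stroke, and no statement that it used the Table 1 codes.

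The check confirms the contradiction and shows what the planning figures depend on. It gives no size for the understatement.

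**The case against.** Three arguments weigh against the point.

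*Table 1 is preliminary and the SAP will refine it.* This is true, and the first extraction is not due until September 2027. But the issue is a conflict between two statements in the protocol, not a detail left open. Adding or removing MI and stroke changes what the endpoint is. Section 9.7 itself says that major changes to primary endpoint definitions would go into a protocol amendment, so the protocol is the place to settle it.

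*No safety information is lost, because MACE captures both.* This stands as a limit on the harm: MACE is itself a primary event with its own rate. It does not supply the missing rate, because MACE also counts unstable angina, heart failure hospitalisation, revascularisation and cardiovascular death.

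*Prior MI or stroke may still be handled.* A reader might infer that patients with an earlier MI or stroke would wrongly stay in the thromboembolic risk set. Section 9.7.2 does not support that: it excludes a respective prevalent condition without tying this to the Table 1 row. Section 9.3.3 lists stroke and coronary or ischaemic heart disease as history variables of their own. How these define prevalence is for the SAP. What remains is that the exclusion should follow whichever endpoint definition is chosen.

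**Conclusion.** The point holds as a contradiction on a primary endpoint. If Table 1 is followed, the rate is too low for the endpoint that Section 9.3.2 defines. This needs only that some patients have an MI or stroke in follow-up as their first event of that endpoint.

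The size is unknown. A reader might take the Table 3 ATE rate as the arterial part and infer that most arterial events are missed. The composite would then lie between 2.50 (complete overlap) and 1.17 + 2.50 = 3.67 (none), an understatement of 1 − 1.17/2.50 = 53% to 1 − 1.17/3.67 = 68%. That is 9.7 to 14.2 events per 3,864 person-years instead of 4.5. The documents do not support this, for the reasons in step 5 of the working. If instead MACE is taken as the ceiling for MI and stroke, the composite is at most 1.17 + 1.41 = 2.58. The understatement is then at most 1 − 1.17/2.58 = 55%, with no lower limit above zero. Both ranges assume that the Table 3 rows share one basis and that 1.17 reflects the Table 1 list. Neither is stated, so neither range should be quoted as a finding.

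**What to change.** Reconcile Section 9.3.2 with the thromboembolic row of Table 1 in one of two ways.

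- **Keep MI and stroke in the endpoint.** Add I21 and the stroke codes to the row, and list VTE and arterial thrombosis as separately coded sub-endpoints. State whether stroke means I63 and I64 only or I60 to I64 as in the MACE row. Section 9.3.2 says stroke without qualification, so the narrower list would be a restriction and should be declared.
- **Keep them out.** Delete MI and stroke from the arterial thrombosis definition in Section 9.3.2 and state that they count only under MACE.

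Under either choice, use the same list for the prevalent-condition exclusion in Section 9.7.2. State which definition the Table 3 rate of 1.17 and the Section 9.5 figures (10 events, HR 6.4) refer to. If MI and stroke are included, obtain a matching background rate and recompute both figures.

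The cost is a text edit, plus one background rate from the Danish data under the first option. The MI and stroke codes are already specified for MACE, so no new data are needed. The change should be made before the first extraction in September 2027.

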# Table 3.Age Standardized Incidence Rates (IRs) of Selected Safety Events of
Interest in Patients with Alopecia Areata (AA) in Denmark (Pfizer
data on file)

Event	IR per 1,000 PYs	PYs Needed to Observe Approximately 1 Event, Given Background IR	PYs Needed to Observe Approximately 1 Event, Given Doubling of Background IR
Any primary malignancy excluding NMSC a	1.13	885	442
Thromboembolic events	1.17	855	427
DVT	0.87	1,149	575
PE	1.09	917	459
ATE	2.50	400	200
MACE b	1.41	709	355
Herpes zoster infection	1.83	546	273
Serious infections c,d	1.89	529	265

a. Incidence rate of malignancy including NMSC in patients with AA not available.

b. Defined by the following outcomes: CV death; acute myocardial infarction; unstable angina; ischemic stroke; haemorrhagic stroke; hospitalization due to heart failure; coronary revascularization by percutaneous intervention or coronary artery bypass graft.

c. Including the following infection types: abscess, bacteraemia, candidiasis and other fungal infections, coronavirus disease of 2019 (COVID-19), female pelvic infections, heart infections (acute rheumatic fever, infectious peri- or myocarditis, endocarditis), human immunodeficiency virus disease, infections of central nervous system, infectious complications of procedures, catheters etc., influenza, intra-abdominal infections, male genital infection, miscellaneous bacterial infection, miscellaneous viral infections, obstetrical infections, other lower-respiratory tract infections, parasitic infections, pneumonia, sepsis, sexually transmitted diseases, skin infections, and viral hepatitis. d. Incidence rate of opportunistic infections in patients with AA not available.

Abbreviations: AA = alopecia areata; ATE = arterial thromboembolism; CV = cardiovascular; DVT = deep vein thrombosis; IR = incidence rate; NMSC = nonmelanoma skin cancer; MACE = major adverse cardiovascular event; PE = pulmonary embolism; PY(s) = person-year(s)

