### PFIZER CONFIDENTIAL

CT24-WI-GL02-RF02 5.0 Non-Interventional Study Protocol Template For Secondary Data Collection Study 01-Aug-2023 Page 30 of 47 The index date and follow-up period will be considered separately with respect to acute-onset outcomes (thromboembolic events, all infection endpoints, MACE) versus delayed outcomes (malignancy excluding NMSC, NMSC, fracture, the neurologic events of interest, MACE). IR and cumulative incidence of each endpoint will be computed after excluding patients with a respective prevalent condition. This lookback period to identify prevalent conditions may be shorter for acute-onset outcomes than for delayed outcomes. For events with long induction/latency period (e.g. malignancy, MACE), events during a prespecified post-index date period may be disregarded and considered prevalent, according to the hypothesized induction/latency periods. The endpoint MACE will be analysed using both approaches. Approaches with and without censoring at treatment discontinuation will be considered.

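### Table 1 counts varicella (ICD-10 B01) as herpes zoster, although the endpoint is named as herpes zoster only

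*Protocol*

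**What the plan says.** Herpes zoster is one of the primary safety events in section 8.2 and is listed again in section 9.3.2. Table 3 gives a background rate for "Herpes zoster infection". None of these places mentions varicella.

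Section 9.3.4 introduces the definitions thus: "Table 1 summarizes the initial operational definitions of the eligibility criteria, the exposure and the endpoints". In the HZ row the diagnosis list starts "B01, B02, H031F, H131M, G051M". No condition is attached to B01, so any one listed code qualifies. The row also accepts antiviral dispensings, but only zoster-specific products, for example "HZ-specific tablet dose 800 mg" in one pack size.

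The footnote to Table 1 takes ICD-10 codes from inpatient encounters in France, and from inpatient or specialist outpatient encounters in Denmark and Sweden. It adds that codes with trailing letters apply only in Denmark.

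Section 9.7.2 states: "IR and cumulative incidence of each endpoint will be computed after excluding patients with a respective prevalent condition". HZ is also a history covariate in section 9.3.3.

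**The concern.** The operational definition does not match the endpoint it serves. Varicella and zoster are separate categories in the classification the protocol cites, and the list takes in both without saying why. If it is followed as written, a coded chickenpox contact during follow-up is reported as a zoster event.

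The same list may be used to identify zoster history or prevalent zoster. A coded chickenpox contact before the index date would then be recorded as past zoster, and could remove the patient from the zoster analysis.

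The expected number of zoster events is small, so even an isolated misclassified case would be visible in the rate. Results are reported by country (section 9.7), which makes each count smaller. Section 9.10 masks counts of 1 to 4, so a reader of the report may not be able to see what a small count is made of.

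**Working it through.** **1. Comparing the places in the protocol**

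- Sections 8.2 and 9.3.2 and Table 3: herpes zoster only.
- Table 1, HZ row, diagnoses: B01 and B02 with equal standing, plus further codes, several of them Denmark-only. In France and Sweden the diagnostic part is therefore essentially B01 and B02.
- Table 1, HZ row, drugs: restricted to zoster-specific strengths or packs, so specificity for zoster was intended.
- Table 1, opportunistic infection row: uses B02 and its subcodes, without B01.
- Table 1, serious infection row: A00-B99 as primary diagnosis with at least one overnight stay. This range already contains B01, so admitted varicella meeting that rule is counted under "Serious infections".

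No passage extends the zoster endpoint to varicella. The meaning of B01 comes from the coding standard the protocol names, not from a definition printed in the protocol.

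**2. The plan's own figures**

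- Person-years per zoster event (Table 3): 1,000 / 1.83 = 546, and at double the rate 1,000 / 3.66 = 273. Both match.
- Ritlecitinib person-years (section 9.5): 0×9 + 74×8 + 96×7 + 110×6 + 127×5 + 144×4 + 161×3 + 123×2 = 3,864. This matches, and with a 1:1 comparator it gives 7,728.

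**3. Expected zoster events**

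- Ritlecitinib: 3,864 × 1.83 / 1,000 = 7.07.
- Both cohorts at 1:1: 7,728 × 1.83 / 1,000 = 14.14.
- Weight of one case: 1 / 7.07 = 14% of the expected ritlecitinib count.

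**4. Illustration only**

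The protocol gives no varicella share. Let f be an assumed share of all HZ events at the background rate, including those found through dispensings, that are varicella only. Zoster-only events are 7.07 × (1 − f), and the overstatement of the zoster rate is f / (1 − f). If a true zoster ratio is 2 and treatment does not affect varicella, the ratio seen is 2(1 − f) + f.

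| Assumed f | Zoster-only events | Overstatement | Ratio seen |
|---|---|---|---|
| 2% | 6.93 | 2.0% | 1.98 |
| 5% | 6.72 | 5.3% | 1.95 |
| 10% | 6.36 | 11.1% | 1.90 |
| 20% | 5.66 | 25.0% | 1.80 |

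These rows also assume that the 1.83 rate was produced with B01 in the list, which the protocol does not say.

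**The case against.** The best defence is that Table 1 is labelled preliminary, that refined country-specific definitions are left to the SAP, and that the SAP may modify the plan. The row also cites a published Danish zoster study, and B01 may have been carried over from there on purpose. This lowers the urgency, since data extraction starts only in September 2027. It does not remove the point, because what is at issue is a specific code that contradicts the named endpoint, not a missing detail. The serious and opportunistic infection rows say their codes will be refined; the HZ row carries no such note.

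The second defence is size, and it largely stands. The exact 95% interval for 7 events is about 2.8 to 14.4, or 0.73 to 3.73 per 1,000 person-years over 3,864 person-years. The overstatements in the illustration lie well inside that width. The hazard ratio is exploratory. With about 14 events in total, the minimum detectable ratio is about 4.4 (assuming 80% power, two-sided 5% and 1:1), so a ratio of 1.8 to 1.98 in place of 2 would not change a conclusion.

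A reader might infer three stronger claims that the protocol does not support:

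- **That chickenpox will remove adolescents as prevalent zoster cases.** Section 9.7.2 fixes no lookback length and allows a shorter one for acute-onset outcomes, which include the infections. Only hospital or specialist records are seen, and only inpatient records in France. The number removed cannot be computed and is probably small.
- **That the error falls mainly on ritlecitinib.** Ritlecitinib is authorised from age 12, and section 7 describes baricitinib as indicated for adults, so some imbalance is possible. Age- and sex-standardised rates, the separate 12-17 subgroup and propensity-score weighting limit it.
- **That the zoster rate is inflated by a known percentage.** Any share is an assumption, and a share of diagnosis-coded events alone would overstate the effect, because dispensings also identify events.

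**Conclusion.** The mismatch is real: B01 stands unconditionally in the definition of a primary safety event named as herpes zoster, and nothing in the protocol justifies it. Followed as written, the definition counts coded varicella as zoster. The effect on history and on prevalent-case exclusion is conditional on the same list being reused there.

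The expected numerical effect is probably small and cannot be derived from the protocol. The point is worth acting on because the expected ritlecitinib count is only about 7, so one case is about 14% of it. That figure rests on the 1.83 rate, on the projected uptake and on no loss to follow-up. Treatment discontinuation would shorten on-treatment person-years and reduce the expected count further.

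**What to change.** - Delete B01 from the HZ event definition, from the HZ history covariate and from any lookback used to exclude prevalent zoster.
- Leave varicella within serious infection, where A00-B99 as primary diagnosis with an overnight stay already captures it.
- If varicella is of interest in itself, report it as a separate line. Renaming the endpoint varicella-zoster would also remove the contradiction, but it would change what is being measured.
- Confirm which codes produced the 1.83 per 1,000 person-years in Table 3. If B01 was included, recompute the rate and the person-years per event without it.
- Label any stated percentage effect of B01 as an illustrative assumption.

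The cost is the removal of one code and one query about the background rate, before extraction begins. Section 9.7 reserves major changes to primary endpoint definitions for a protocol amendment, so the sponsor should record whether this correction counts as one.
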